5.5.4. DESS scale and C-SSRS data

Discontinuation-Emergent Signs and Symptoms scale and C-SSRS data will be summarized by descriptive statistics at each visit and by treatment group unless otherwise specified. Change from baseline at each visit will be presented using descriptive statistics by treatment group for C-SSRS. Please see Section 3.8.6 for details on DESS.

All DESS scale and C-SSRS data will be presented in a data listing.

5.5.5. 12-Lead Electrocardiograms

ECG parameters (Heart Rate, RR interval, QRS Duration, QT Interval, QTcF) will be assessed according to the schedule of assessments in Table 1 of the protocol.

12-lead ECG recordings will be performed in triplicate (at approximately 1-min intervals between each of the three recordings) at baseline, and single ECG for rest of visits.

QT corrected by Fridericia's formula is recommended: $QTcF = QT/RR^{0.33}$.

Actual value, change from baseline, and percent change from baseline at each visit (timepoint if applicable) will be presented using descriptive statistics by treatment group.

Shift of ECG overall interpretation from baseline to end of treatment visit will be prepared with number and percentage of subjects being reported with Normal, Abnormal, Abnormal Clinically Significant, and Not Done.

The QTcF interval will be summarized by the frequencies of subjects with absolute value and/or change from baseline using the criteria identified below:

- <450
- \geq 450 to < 480
- ≥ 480 to < 500
- ≥ 500
- <30 increases from baseline
- 30 to ≤ 60 increases from baseline
- > 60 increases from baseline

Subjects with abnormal ECG results, regardless of clinical significance, will be identified in data listings with flags for abnormalities.

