- e Baseline evaluations will be performed on Day -1. Patients will be instructed to take the first dose of double-blind study drug the day after baseline evaluations (ie, on Day 1), and will be instructed to take double-blind study drug for the remainder of the 6-week treatment period.
- f For patients who discontinue early from the study, safety and efficacy determinations designated for Day 42 will be performed on the last day the patient takes a full dose of study drug or as soon as possible thereafter, but within 3 days of their last dose in any event.
- g At Visit 1, two brief ICFs will be obtained for the purpose of genotyping and biobanking, separately. A full ICF must be obtained at Visit 2.
- h Refer to Appendix 2 Preliminary Diagnosis Checklist
-  A separate blood sample (6 mL) will be collected for PGx (eg, determination of DGM4 status at Screening and for future research at Visit 5).
- The PRDF Checklist must be completed by the patient and reviewed by the rater 2 prior to CGI-S assessment. The baseline checklist entry must be compared by rater 2 against post-baseline entry to refresh the knowledge of patient's baseline condition prior to CGI-I assessment.
- k C-SSRS baseline/screening version
-  C-SSRS since-last-visit version
- m For randomized patients who complete the study or discontinue early, the DESS scale will be completed daily by the patient for 14 days post-last dose.
- n Vital signs should be taken prior to blood draws when applicable and include supine (after at least 5 min rest) and standing (after 1 min and 3 min standing), BP and heart rate, respiration rate, and temperature. Vital signs can be repeated for up to 3 occurrences after Visit 2 to see if values return to normal range, but any abnormality must be resolved by the Baseline Visit.
- o ECG recordings will be completed prior to blood draws when applicable and will be performed in triplicate (at 1-minute intervals between each of the three recordings) for baseline. Single ECG will be performed for rest of the timepoints.

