3. GENERAL STATISTICAL CONSIDERATIONS

3.1. General Methods

Statistical analysis will be performed using SAS® software Version 9.4 or later (SAS 2001).

For continuous variables, descriptive statistics will include the number of subjects (n), mean, SD, median, minimum, and maximum. Frequencies and percentages will be displayed for categorical data. Percentages by categories will be based on the number of subjects including missing data, ie, will add up to 100%.

The estimated mean and median for a set of values should be calculated to one more decimal place than the raw (observed) data and rounded appropriately. Standard errors (SE) (or SD) should be calculated to two decimal places beyond the raw (observed) data and rounded appropriately. The decimal place for minimum and maximum should be the same as raw (observed) data. Percentage values should be reported with one digit to the right of the decimal point. When numerator value is "0," it should be displayed as "0." Further, a maximum of two decimal places will be used for all summary statistics unless otherwise specified.

Summaries presented by visit will be based on the scheduled assessments as planned in the protocol. Unscheduled assessments will not be included in the by-visit summary tables, however, will be included in the listings. Any unscheduled visit that falls within a visit window period without a scheduled visit will be used in summary tables. The summary tables and listings will be presented by DGM4 status (positive/negative) where noted, treatment group, and overall. The treatment groups are defined as:

- Placebo QD
- Liafensine 1 mg QD
- Liafensine 2 mg QD
- Liafensine 1 mg and 2 mg QD

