3.4. Study Visits

Study visits in the electronic data capture (EDC) datasets include Screening 1 (Visit 1) and Screening 2 (Visit 2), Day -1 (Visit 3), Day 7 (Visit 4), Day 14 (Visit 5), Day 28 (Visit 6), Day 42 (Visit 7/End of Treatment [EOT]), Day 14 and Day 28 post-last dose follow-up, and any unscheduled visits. Study visits will be windowed so that data recorded at any time have the potential to be included in summaries. The following visit window conventions will be followed:

Visit	Visit Number	Day	Window
Screening 1	1		
Screening 2	2		
Visit 3	3	-1	-1 to 3
Visit 4	4	7	4-10
Visit 5	5	14	11–20
Visit 6	6	28	21–34
Visit 7/EOT	7	42	35-49

Unscheduled visits will not be used in the summary by visit unless otherwise specified, the unscheduled visit values will be considered in the summary of worst change from baseline.

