3.8.5. Columbia-Suicide Severity Rating Scale

Columbia-Suicide Severity Rating Scale (C-SSRS) was designed to quantify the severity of suicidal ideation and behavior (Posner 2011). C-SSRS is a measure used to identify and assess individuals at risk for suicide. Questions are phrased for use in an interview format but can be completed as a self-report measure if necessary. C-SSRS measures four constructs: the severity of ideation, the intensity of ideation, behavior, and lethality. It includes "stem questions," which if endorsed, prompt additional follow-up questions to obtain more information. There are four versions of the scale available, including: 1) Baseline/screening version, which allows practitioners to gather a lifetime and recent 12 months history of suicidal ideation and/or behavior; 2) Since Last Visit version for assessment of suicidal thoughts and behaviors since C-SSRS was last administered; 3) Screen version, a shortened version of the full form (3-6 questions) most commonly used in clinical triage settings; 4) Risk Assessment Page, which provides a checklist of protective and risk factors of suicidality.

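### SAP 5.5.4 summarises the C-SSRS by a change from baseline with no defined score or baseline, and never counts the patients per arm with any post-baseline suicidal ideation or behaviour

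*SAP*

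**What the plan says.** SAP 5.5.4 contains three C-SSRS outputs:

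- a by-visit summary: "C-SSRS data will be summarized by descriptive statistics at each visit and by treatment group unless otherwise specified"
- a by-visit change: "Change from baseline at each visit will be presented using descriptive statistics by treatment group for C-SSRS"
- a listing: "All DESS scale and C-SSRS data will be presented in a data listing"

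Protocol 8.3.4 likewise asks only for descriptive statistics by visit and treatment.

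SAP 3.8.5 describes the instrument: "C-SSRS measures four constructs: the severity of ideation, the intensity of ideation, behavior, and lethality". It mentions stem questions and several versions of the form, but gives no total score or coding rule. SAP 3.2 defines baseline as the last value before first dose, for laboratory, ECG, vital-sign and efficacy values. The C-SSRS is in none of these groups.

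Protocol Table 1 assigns the baseline/screening form to Visit 2. From Day -1 through both follow-up contacts the footnote reads "C-SSRS since-last-visit version".

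On unscheduled data, SAP 3.4 states: "Unscheduled visits will not be used in the summary by visit unless otherwise specified". It keeps those values for a summary of worst change. SAP 3.1 makes one exception: an unscheduled visit is used when its window holds no scheduled one.

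**The concern.** The C-SSRS is listed as a safety endpoint in both documents, and the first safety objective is a comparison with placebo. Exclusion 27 removes patients with past-year suicidal behaviour, or with past-year active ideation with plan and intent. Baseline should therefore sit near the floor for the gravest categories, and the safety question is how many patients in each arm develop them.

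The planned tables do not answer that. A change score with no stated variable could be programmed in several ways. A mean or median change can let mild improvement in some patients offset new severe ideation in others. Visit-by-visit tables never combine a patient's assessments. Taken as written, the plan yields no per-patient incidence and no between-arm C-SSRS contrast in a trial of an antidepressant.

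**Working it through.** The plan gives no figure for the C-SSRS analysis, so there is none to reproduce. The only planned number used is arm size: about 180 randomised 1:1:1 (SAP 2.1), so 180/3 = 60 per arm.

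**1. Is the change defined?** Three things are needed.

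- *A variable.* SAP 3.8.5 gives four constructs and no score.
- *A baseline.* SAP 3.2 does not name the C-SSRS. If its last-value rule is borrowed, baseline is normally the Day -1 form, and the Visit 2 recall of lifetime and 12 months does not enter the change.
- *A comparable period.* From the Table 1 visit days, the since-last-visit form covers up to about three weeks at Day -1 (longer with a prolonged washout), about one week at Days 7 and 14, and about two weeks at Days 28 and 42.

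The first two are missing and the third is not met.

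**2. What can a mean change show?** Assume ideation coded 0 to 5, which the documents do not state, and 60 patients. Let k patients move from 0 to 5, m move from 1 to 0, and the rest stay unchanged.

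Mean change = (5k − m)/60.

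| k (new cases) | m (improvers) | Mean change | Newly affected |
|---|---|---|---|
| 1 | 5 | (5 − 5)/60 = 0.00 | 1/60 = 1.7% |
| 2 | 10 | (10 − 10)/60 = 0.00 | 2/60 = 3.3% |
| 5 | 25 | (25 − 25)/60 = 0.00 | 5/60 = 8.3% |

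In the second row 60 − 12 = 48 patients are unchanged, so the median is also 0. The maximum is +5 in every row. It shows that at least one patient worsened, but does not separate one case from five.

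**3. Do by-visit frequencies repair this?** SAP 3.1 says: "Frequencies and percentages will be displayed for categorical data". Treat the items as categorical. Table 1 has six post-baseline C-SSRS assessments: Days 7, 14, 28 and 42, and two follow-ups. Suppose all 60 patients attend and each table shows one affected patient, 1/60 = 1.7%. If it is the same patient throughout, any-time incidence is 1/60 = 1.7%. If it is a different patient each time, it is 6/60 = 10%. The six tables are identical in both cases.

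**4. Unscheduled assessments.** Under SAP 3.1 they enter a by-visit table only where the window has no scheduled visit. Otherwise SAP 3.4 keeps them for a worst-change summary, which 5.5.4 does not request for the C-SSRS.

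**5. What the SAP does for other safety data.**

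| Data | Planned beyond by-visit descriptive statistics |
|---|---|
| Liver tests (5.5.2) | Threshold categories; risk difference vs placebo with 95% CI |
| Chemistry and haematology (5.5.2) | Shift from baseline to maximum post-baseline value |
| Heart rate, orthostatic BP (5.5.3) | Patients over a threshold at each visit; risk difference with 95% CI |
| ECG (5.5.5) | Shift table; QTcF categories |
| DESS (3.8.6) | Patients by score category each day; CMH test |
| C-SSRS (5.5.4) | Listing only |

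**The case against.** The best defence is that the documents already keep the cases visible, and much of it stands.

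- **Frequencies are available.** The stem questions are categorical, so SAP 3.1 and Protocol 8.3.4 point to counts and percentages by visit. That answers the averaging problem for those items, but not step 3.
- **The mean is not reported alone.** SAP 3.1 states: "For continuous variables, descriptive statistics will include the number of subjects (n), mean, SD, median, minimum, and maximum". Worsening would show in the maximum, so a reader who infers that the table would hide any deterioration goes too far. Only the number of cases is missing.
- **Cases are not lost.** Every record is listed. Suicidal behaviour reported as an adverse event would be counted once per patient in the TEAE tables. The documents do not link a positive C-SSRS answer to adverse event reporting, however, so those tables are not a C-SSRS comparison.
- **Cancellation concerns ideation.** With past-year behaviour excluded, there is little baseline behaviour to offset new behaviour.
- **Unequal recall is the same in every arm.** All arms share one schedule, so this does not bias the between-arm comparison. It affects what a change from baseline means.

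Two stronger readings are tempting. One is that change from baseline is an invalid measure for this scale. The documents say no such thing; they show that it is undefined here. The other is that unscheduled assessments are dropped. SAP 3.1 and 3.4 each give them a use, though neither provides a C-SSRS worst-case table.

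**Conclusion.** The point holds as a gap in the safety analysis. Change from baseline in the C-SSRS is undefined in this SAP and unsuitable as the only planned summary of change. Neither by-visit means nor by-visit frequencies give the number of patients per arm with any post-baseline ideation or behaviour.

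The size can only be illustrated. Under the assumed 0-to-5 coding and 60 per arm, a mean change of 0.00 is compatible with 1.7% to 8.3% newly affected. One affected patient per visit is compatible with 1.7% to 10% at any time. These figures show what the tables cannot distinguish; they do not forecast this trial's results.

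The documents do not support saying that cases would disappear from the report. They would be listed, but not counted per patient across the study or compared with placebo on this scale. Efficacy analyses and clinical conduct are unaffected.

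**What to change.** In SAP 5.5.4, replace the C-SSRS change-from-baseline summary with patient-level counts:

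1. By arm, n (%) with any post-baseline suicidal ideation, by worst category, and n (%) with any suicidal behaviour. Report treatment and follow-up periods, and include unscheduled assessments.
2. A shift table from a stated pre-treatment reference to the worst post-baseline category. Show the Visit 2 recall form and the Day -1 form as separate references, because their recall periods differ. Merging them would set 12 months of recall against one or two weeks, and could hide the return of earlier ideation.
3. The risk difference against placebo with a 95% CI, as already planned for liver tests and vital signs. The SAP names no interval method, and counts near zero make that choice matter.

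Keep the listing. The cost is SAP wording and two table shells, with no new data. The intervals will be wide because events will be few, so the tables should be read as descriptive.

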5.5.6. Physical and Neurological Exam

Physical and Neurological exam data will be presented in a data listing.

5.6. Exploratory Analysis

5.6.1. Treatment Response in DGM4-Positive Patients

Treatment response is defined as \geq 50% improvement from baseline in MADRS total score at Day 42 (Visit 7) in DGM4-positive patients. Response rate and corresponding 95% confidence interval for each treatment group will be derived by using Clopper-Pearson method (Clopper 1934). The comparison of response rate between treatment groups will be carried out using the CMH test. The percentage of subjects achieving response in MADRS by visit will be displayed in a bar chart.

5.6.2. Remission in DGM4-Positive Patients

Remission is defined as MADRS total score ≤ 10 at Day 42 (Visit 7) in DGM4-positive patients. Remission rate will be analyzed using the same methodology as described in Section 5.6.1. The percentage of subjects with remission by visit will be displayed in a bar chart.

5.6.3. Change in MADRS Anhedonia Subscale and Individual Items from Baseline to Day 42, in DGM4-Positive Patients

Change in MADRS anhedonia subscale and individual items from baseline (Visit 3, Day -1) to Day 42 (Visit 7) will also be analyzed in an exploratory manner, using the MMRM model without imputation similar to the one used in sensitivity analysis (2) for the primary efficacy endpoint described in Section 5.4.1.3. Anhedonia score is the sum of MADRS items 1 (reported sadness), 2 (apparent sadness), 6 (concentration difficulties), 7 (lassitude), and 8 (inability to feel).

5.6.4. Change in MADRS Total Score from Baseline to Day 42, in DGM4-Negative Patients

The change in MADRS total score from baseline to Day 42 (Visit 7) in DGM4-negative patients will be summarized using descriptive statistics.

5.6.5. Change in MADRS Total Score from Baseline to Day 42 in Liafensine 1 mg QD Group and 2 mg QD Group, in both DGM4-Positive and DGM4-Negative Patients

The change in MADRS total score from baseline to Day 42 (Visit 7) in liafensine 1 mg and 2 mg QD groups in both DGM4-positive and DGM4-negative patients will be analyzed using descriptive statistics. The treatment effects between the DGM4-positive and negative patients will be compared primarily in descriptive fashion to examine the trend and may be evaluated by including the interaction of DGM4 status and treatment group in the mixed model.

5.7. Pharmacokinetics

5.7.1. Plasma Concentrations

Plasma concentrations of liafensine and its major metabolite 821007 will be listed by subject and time of collection.

6. CHANGES FROM ANALYSES PLANNED IN THE PROTOCOL

Changes from the protocol-specified analyses are listed in Table 4.

Protocol	SAP	Justification
Section 8.3.3.1: The family- wise type I error rate will be controlled at a fixed 1-sided alpha level of 0.025 using a closed testing procedure for multiple dose comparisons and multiple endpoint comparisons in DGM4-positive patients.	Section 3.7: All statistical tests for the treatment comparison of efficacy endpoints will be based on a 1-sided alpha level of 0.05.	In this Phase 2b study, the sample size was not powered for testing superiority with multiplicity adjustment for each dose.
Section 8.3.3: The primary efficacy analysis will be performed in DGM4-positive patients at 2-sided significance level of 0.05 using a mixed model for repeated measures (MMRM) that includes the fixed effects of treatment, visit (categorical covariate), treatment-by-visit interaction, baseline MADRS total score (continuous covariate), and region.	Section 5.4.1.2: The primary method will be mixed model for repeated measures (MMRM) with imputation assuming missing at random (MAR), ie, a hypothetical strategy per ICH E9(R1). Hence, missing values will be imputed with non- missing values in the same treatment group. A fully conditional specification and predictive mean matching method will be used in the imputation. The following variables will be included in the imputation model: region, baseline MADRS score, and change from baseline at Weeks 1, 2, 4, and 6. One hundred fully imputed datasets will be created. The MMRM described in Section 5.4.1.2 will be used for treatment comparisons. Treatment effects (difference in LS means between treatment arms) from these 100 analyses will be combined to generate the final results using Rubin's method with SAS MIANALYZE procedure.	 With multiple imputation, all subjects in the full analysis set will have a value at the primary time point, ie, Day 42, for treatment comparisons. Since the original method in the protocol assumes missing at random, the same assumption will be used in multiple imputation. This method allows for performing a tipping point analysis to assess the robustness of the results under the MAR assumption.

7. **REFERENCES**

Buuren SV. Multiple imputation of discrete and continuous data by fully conditional specification. Stat Methods Med Res. 2007;16(3):219–242.

8. APPENDIX: SAMPLE SAS CODES

The sample SAS codes provided in this section are for reference only. The actual SAS codes to generate the tables will be checked through QC process. For sensitivity analyses using RAS, use the dataset flag for RAS and exclude GPN*base, ie, treatment-by-baseline-score interaction, in the model statement in Proc Mixed.

8.1. SAS Code for Multiple Imputations Based on the Non-missing Values in the Same Arm with FCS and REGPMM Options

```
%let nimpute=100;
%let seed=10401;
proc sort data=adqs4 out=adqs5;
where avisitn in (40 50 60 70) and dgmn=1 and gpn^{3};
by trt01pn usubjid dgmn gpn region base avisitn;
run:
proc transpose data=adqs5 out=cfb;
 by GPN usubjid dgmn region base;
 var chg;
 id avisitn;
run;
*** Imputation using fully conditional specification and predictive mean matching methods;
proc mi data=cfb(rename=( 40=cfb1 50=cfb2 60=cfb4 70=cfb6)) nimpute=&nimpute
seed=&seed out=fcs;
 by GPN;
 class region;
 var region base cfb1 cfb2 cfb4 cfb6;
 FCS REGPMM;
run:
```

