2.3. Sample Size Calculation

Eligible patients will be randomized 1:1:1 to receive placebo QD, liafensine 1 mg QD, or liafensine 2 mg QD. The primary analysis is to assess treatment difference in MADRS total score change from baseline (Visit 3, Day -1) to Visit 7 (Day 42), between the combined liafensine 1 mg QD and 2 mg QD doses vs placebo, in DGM4-positive patients. A sample size of 47 randomized DGM4-positive patients per arm is sufficient to detect a 4.5-unit difference between the combined liafensine 1 mg QD and 2 mg QD and 2 mg QD and 2 mg QD treatment groups and the placebo treatment group in the change in MADRS total score from baseline to Day 42 with 80% power at the 2-sided 0.05 alpha level, assuming a standard deviation (SD) of 9 units.

To compensate for potential loss of power due to randomized patients who do not take at least one dose of study drug or who do not have a post-randomization efficacy evaluation (~5%), a total of approximately 150 DGM4-positive patients (50 DGM4-positive patients per arm) will be randomized.

To examine trend in the total patient population and in the subgroup of DGM4-negative patients in order to evaluate DGM4 as a potential biomarker for predicting response to liafensine, approximately 20% additional DGM4-negative patients (10 per arm, total 30) will also be randomized. The sample size of 30 randomized patients in the DGM4-negative group is not estimated based on formal statistics in terms of power and alpha level.

Sample size re-estimation may be conducted if the percentage of missing data at Day 42 visit is higher than expected and/or if the observed variance is higher than the one assumed in the sample size estimation.

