4. ANALYSIS SETS

4.1. Randomized Analysis Set

The randomized analysis set (RAS) includes all randomized patients in this study. This analysis set will be used for a sensitivity analysis of the primary and key secondary efficacy endpoints for DGM4-positive patients. The RAS population will be analyzed by treatment randomization regardless of the actual treatment received.

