The same model in the primary analysis will be used without imputation using the treatment policy strategy per ICH E9(R1) (Polverejan 2023). This analysis will be used to assess the impact of imputing missing values based on the MAR assumption.

3. MMRM with imputation using pattern mixture model

This sensitivity estimator will be using a control-based multiple imputation method (Ratitch 2013). This sensitivity analysis does not rely on the MAR assumption. Data collected after initiation of prohibited medications will not be used unless otherwise specified. Missing data due to all ICEs will be handled per specifications below unless otherwise specified.

In this sensitivity analysis, imputation will be implemented using SAS MI procedure with FCS statement and REGPMM option, as well as MNAR statement with MODELOBS option to identify observations from the placebo arm for deriving the imputation models, ie, assuming all missing data will have a profile that equals the profile of the placebo arm for all time points. The variables to be used in the imputation are region, baseline values, and change from baseline values observed at Weeks 1, 2, 4, and 6.

One hundred fully imputed datasets will be created. The MMRM described in Section 5.4.1.2 will be used for treatment comparisons. Treatment effects (difference in LS means between treatment arms) from these 100 analyses will be combined to generate the final results using Rubin's method with SAS MIANALYZE procedure.

A tipping point analysis for this sensitivity analysis will also be conducted to assess the robustness of the result. The same steps described in the first sensitivity analysis will be followed.

4. Sensitivity Analyses based on RAS

A set of sensitivity analyses listed below will be performed using DGM4-positive patients in RAS. The same MMRM in the primary and sensitivity analyses described above will be carried out with the exclusion of the following fixed effect: treatment by baseline MADRS total score. In other words, the model will include the fixed effects of treatment, visit (categorical covariate), treatment by visit interaction, baseline MADRS total score (continuous covariate), and region.

The following analyses will be performed in this set of sensitivity analyses:

- 1) The primary analysis, as well as the 1st and 2nd sensitivity analyses based on FAS will be repeated using RAS.

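### The RAS repeat of the MMRM without imputation cannot add patients who have no post-baseline MADRS score, and the sample code does not ensure that they reach the imputed RAS repeats

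*SAP*

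**What the plan says.** SAP Section 4.1: "The randomized analysis set (RAS) includes all randomized patients in this study". Section 4.2 defines the FAS more narrowly: a patient must have been dosed at least once and have an efficacy evaluation after randomisation. The RAS therefore adds patients who were never dosed or were never evaluated after randomisation.

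Section 5.4.1.3, item 4, says that the primary analysis, "as well as the 1st and 2nd sensitivity analyses based on FAS will be repeated using RAS". The first of these is the tipping point and the second is the MMRM without imputation. The third sensitivity analysis gets its own RAS version, with imputation rules that depend on why the patient stopped.

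The opening of Section 8 instructs: "For sensitivity analyses using RAS, use the dataset flag for RAS", and also drops the treatment-by-baseline interaction. It calls the code a reference and says that the final programs go through QC. Section 8.1 selects records by "where avisitn in (40 50 60 70) and dgmn=1" (visits 40 to 70 are Days 7, 14, 28 and 42), then transposes to one row per patient and runs PROC MI. Section 8.4 applies the same filter before the placebo-based imputation.

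Section 3.2 ties baseline to the first dose, and Section 3.3 ties study day to the start of treatment.

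**The concern.** A RAS analysis is informative about exclusions after randomisation only if the excluded patients contribute to it. Two features work against that.

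- **The non-imputed MMRM.** A patient with no post-baseline change adds nothing to the likelihood, however the dataset is laid out.
- **The printed code for the imputed runs.** The filter acts on visit records. A patient with none is lost before the transpose, and switching the population flag cannot restore rows that do not exist.

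If both apply, RAS and FAS runs use essentially the same patients under slightly different models. Agreement would then say nothing about the exclusions, and a small difference would reflect the dropped interaction term. The RAS tipping point has the same weakness, because Section 8.7 shifts only values flagged as imputed and an absent patient is never shifted.

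**Working it through.** **1. The plan's own figures (SAP Section 2.3).** The inputs are: "A sample size of 47 randomized DGM4-positive patients per arm is sufficient to detect a 4.5-unit difference"; "with 80% power at the 2-sided 0.05 alpha level, assuming a standard deviation (SD) of 9 units"; and "Eligible patients will be randomized 1:1:1 to receive placebo QD, liafensine 1 mg QD, or liafensine 2 mg QD". Pooling the two active arms gives 2:1 against placebo.

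- Placebo n = (1 + 1/2) × [9 × (1.960 + 0.842) / 4.5]² = 47.09, against 47 stated. Power at 47 per arm is 79.9%. The figure is reproduced.
- Inflation: 47 / 0.95 = 49.5, so 50 per arm and 150 in total, as stated.

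**2. How many patients are at issue.** Section 2.3 allows for patients who are never dosed or "who do not have a post-randomization efficacy evaluation (~5%), a total of approximately 150 DGM4-positive patients".

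- 0.05 × 150 = 7.5, so 7 to 8 patients, or 2 to 3 per arm.
- If the share were 2% to 10% (assumed range): 3 to 15 patients.

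These are planning figures, not observed counts.

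**3. MMRM without imputation.** The outcome is change from baseline at Days 7, 14, 28 and 42. A patient with all four missing contributes no observation. The one possible exception is a never-dosed patient with later MADRS scores, but Sections 3.2 and 3.3 leave that patient's baseline and study day undefined. Section 4.1 also intends the RAS for the key secondary endpoint. CGI-S is analysed without imputation (Section 5.4.2), so the same limit applies there.

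**4. Imputed repeats, code as printed.** The Section 8.1 filter and transpose were run on a mock dataset of 150 patients, 9 of them (150 − 3 × 47) with a baseline record only.

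| Input layout | Patients reaching PROC MI | Patients usable by MMRM without imputation |
|---|---|---|
| Visit records only | 141 | 141 |
| One row per randomised patient per visit, blanks allowed | 150 | 141 |

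The layout decides the imputed runs. It makes no difference to the non-imputed run.

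**5. What entry could do to the estimate.** If a fraction f of the active patients is given a placebo profile, a 4.5-point effect becomes 4.5 × (1 − f):

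- f = 2%: 4.41
- f = 5%: 4.275
- f = 10%: 4.05

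Same-arm imputation of patients with baseline data only adds little information, so even a correctly built RAS repeat of the primary analysis should track the FAS.

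**6. Tipping point (illustration, ignoring changes in standard error).** Assume that 10% of FAS values at Day 42 are imputed. With the added 5% present, the share shifted is 0.05 + 0.95 × 0.10 = 14.5% rather than 10%. The tipping shift would then be about 0.10 / 0.145 = 0.69 of that found without them. With 5% assumed it is 0.05 / 0.0975 = 0.51, and with 20% it is 0.20 / 0.24 = 0.83.

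**The case against.** The strongest reply is that sample code is not the specification. Section 8 says that the code is a reference and that production programs are checked. The governing text puts every randomised patient in the RAS, and the RAS version of the third analysis says that all randomised early discontinuers with missing data are classified and imputed. The dataset adqs4 is clearly derived (it holds pooled-arm records), and it may contain blank visit rows. All of this stands, and it limits what can be claimed about the imputed runs. It does not close the gap: nothing else in the SAP says how a patient with no visit record enters, so QC against this text would not necessarily catch the loss.

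A reader might go further and infer that the added patients never enter any RAS analysis, or that all RAS results must match the FAS. The documents do not support either inference.

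- The imputed repeats depend on a layout that the SAP leaves open.
- Section 8.5 works from its own subject-level inputs (cfb0, cfb1), whose construction is not shown.
- The RAS version of the third analysis uses cause-specific rules where the FAS version imputes from placebo, so the two need not agree.
- Changing the flag does not reproduce the FAS model, because the interaction is also dropped.

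A reader might also take the purpose of the RAS runs as known. The SAP version history says only that they answer regulatory comments, and it does not reproduce those comments.

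Finally, it is fair to say that any MMRM without imputation ignores patients with no outcome. That makes the RAS repeat nearly redundant rather than wrong, and the SAP should say so.

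**Conclusion.** The point holds in two parts of different strength.

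- **Certain:** the RAS MMRM without imputation adds no patient who lacks a post-baseline MADRS score, so it is not evidence about post-randomisation exclusions.
- **Conditional:** in the RAS repeats of the primary analysis and the tipping point, such patients are missing from PROC MI if the printed code is followed and adqs4 has no blank visit rows. For the cause-specific analysis in Section 8.5 the question is open.

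The size is modest: 7 to 8 patients at the SAP's 5% (3 to 15 at an assumed 2% to 10%), in sensitivity analyses only. The primary analysis is unaffected. Under a placebo profile for 5% of active patients, a 4.5-point effect would move to about 4.28. The change is worth making because it is cheap and because the RAS runs as described may not show what a reader would take them to show.

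**What to change.** 1. Build the RAS imputation input from the list of randomised patients: one row per DGM4-positive patient with region and baseline, joined to the visit changes, blanks allowed. Apply this to Sections 8.1 and 8.4, and show how cfb0 and cfb1 are built in Section 8.5.
2. Define baseline for never-dosed patients, for example as the last value on or before randomisation. Protocol Table 1 schedules MADRS and randomisation at the same visit. State how visit windows are set for these patients.
3. State that the RAS MMRM without imputation uses only patients with at least one post-baseline score and is not evidence about the excluded patients. Say the same for any RAS run of CGI-S.
4. Specify one RAS analysis in which the patients in the RAS but not the FAS are imputed from placebo.
5. Report, by arm, how many of these patients entered each RAS run.

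The cost is a few lines of code, a short SAP clarification and possibly a slightly smaller sensitivity estimate. No new data are needed.
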